9.4.3 Analysis of Secondary Endpoints

The secondary PK endpoints are the following parameters in plasma for metformin:

- t_{\max} , $t_{1/2}$, λ_Z , $AUC_{0-\infty}$, $AUC_{\%extra}$, CL/f , V_z/f .

For t_{\max} , the Hodges-Lehmann estimates [20] for the pairwise treatment differences and the corresponding 90% CIs according to the Tukey method will be calculated.

The mixed model as described above will also be applied to $AUC_{0-\infty}$. A 90% CI will be calculated for the ratios of geometric means of the test IMP and reference IMP.

All secondary endpoints will be summarized descriptively by group and treatment in the PK Population.

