11.5 Presentation of PK Parameter Data

Pharmacokinetic parameter data will be descriptively summarized using: N, Mean, SD, CV%, Min, Median, Max, geometric mean (GeoMean), the geometric CV% (GeoCV%), and the 95% CI for the GeoMean (LCI 95% GM, UCI 95% GM).

Descriptive statistics of PK parameter data will be calculated using full precision values, and rounded for reporting purposes only.

The following conventions will be applied when reporting descriptive statistics of PK parameter data:

Mean, Min, Median, Max, GeoMean, 95% CI:	3 significant digits
GeoMean ratio:	2 decimal places
SD:	4 significant digits
CV%, GeoCV%:	1 decimal place

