16.2 Secondary Endpoint Analyses

All secondary PK endpoints will be descriptively summarized as described in [Section 11](#). The secondary PK endpoints are the following parameters in plasma for metformin:

t_{max} , $t_{1/2}$, λ_Z , $AUC_{0 \rightarrow \infty}$, $AUC_{extra\%}$, $CL_{f/f}$, $V_{Z/f}$.

For t_{max} , the Hodges-Lehmann estimates for the treatment differences and corresponding 90% CIs according to the Tukey method will be calculated.

The mixed-effects model for treatment comparison as described for the primary endpoints will also be applied to $AUC_{0 \rightarrow \infty}$. The ratios of geometric means and corresponding 90% CIs for Treatment A/Treatment B will be estimated separately for fed and fasted treatments. Graphs of individual $AUC_{0 \rightarrow \infty}$ values and geometric mean will be presented by treatment and food consumption condition.

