CL _f	The apparent total body clearance of drug following extravascular administration, taking into account the fraction of dose absorbed. CL _f = Dose _{p.o.} /AUC _{0→∞} . The predicted AUC _{0→∞} will be used. The dose amount to be used for this calculation is 500 mg. Units: L/h.
C _{max}	Maximum observed concentration, taken directly from the observed concentration-time profile. Units: ng/mL.
t _{max}	The time to reach the maximum observed concentration (unless otherwise defined, take the first occurrence in case of multiple/identical C _{max} values). Units: h.
t _{1/2}	Apparent terminal half-life. t _{1/2} = ln (2)/λ _z . Units: h.
V _{z/f}	The apparent volume of distribution during the terminal phase following extravascular administration, based on the fraction of dose absorbed. V _{z/f} = Dose/*AUC _{0→∞} *λ _z) following single dose. The predicted AUC _{0→∞} will be used. Units: L.

λ_z	Terminal elimination rate constant. Determined from the terminal slope of the log-transformed concentration curve using linear regression on terminal data points of the curve. Units: h^{-1} .
-------------	--

The predicted $\text{AUC}_{0 \rightarrow \infty}$ will be reported and used in the determination of other parameter estimates, i.e., $\text{AUC}_{\text{extra}\%}$, CL/f , and $\text{V}_{\text{z/f}}$. The following PK parameters will be calculated for diagnostic purposes and listed, but will not be summarized:

- The time interval (h) of the log-linear regression (λ_z lower, λ_z upper) to determine λ_z .
- Number of data points (N_λ) included in the log-linear regression analysis to determine λ_z .
- Goodness-of-fit statistic (Rsq) for calculation of λ_z .

The regression analysis should contain data from at least 3 different time points in the terminal phase consistent with the assessment of a straight line on the log-transformed scale. Phoenix WinNonlin best fit methodology will be used as standard. The last quantifiable concentration should always be included in the regression analysis, while the concentration at t_{max} and any concentrations below the LLOQ which occur after the last quantifiable data point should not be used.

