The Rsq should be ≥ 0.800 and the observation period over which the regression line is estimated should be at least two-fold the resulting $t_{1/2}$ itself. If these criteria are not met, then the rate constants and all derived parameters (e.g., $\text{AUC}_{0 \rightarrow \infty}$, $\text{AUC}_{\text{extra}\%}$, CL/f , $t_{1/2}$, and $\text{V}_{\text{z/f}}$) will be included in the parameter outputs and descriptive statistics but will be flagged and discussed appropriately. Any flags should be included in the study specific SDTM.

To ensure a reliable estimate of the extent of exposure in pivotal trials (e.g., BE), $\text{AUC}_{\text{extra}\%}$ should be less than or equal to 20.0%. If $\text{AUC}_{\text{extra}\%}$ is greater than 20.0%, all parameters derived using λ_z (i.e., $\text{AUC}_{0 \rightarrow \infty}$, $\text{AUC}_{\text{extra}\%}$, λ_z , $t_{1/2}$, $\text{V}_{\text{z/f}}$, and CL/f) will not be included in the calculation of descriptive statistics or statistical analyses.

The dose amount for IMP administered is that of the active, free drug substance only, and is synonymous with the measured analyte. No adjustment for the dose amount value of IMP will be applied when 'dose' is used in calculating PK parameters with formulas needing a dose value.

The Phoenix WinNonlin NCA Core Output will be provided in a separate listing.

17 Safety Evaluation

The subsections in this section include specifications for summarizing safety endpoints that are common across clinical trials such as adverse events, laboratory tests, ECG recordings and vital signs. Safety analyses will be done on the Safety Population. All safety data will be listed in individual subject listings by group, treatment sequence and subject.

All safety variables will be analyzed using descriptive statistics. For the evaluation of safety parameters, the continuous variables will be summarized descriptively by N, mean, median, SD, Q1-Q3, and minimum and maximum values.

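### SAP 16.3.2 drops AUCextra% from its own summary when it exceeds 20.0%, so the planned Mean and Max for this secondary endpoint are cut off at the limit

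*SAP*

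**What the plan says.** AUCextra% is one of the secondary PK endpoints in Protocol 9.4.3 and SAP 16.2. The protocol states: "All secondary endpoints will be summarized descriptively by group and treatment in the PK Population". The SAP states: "All secondary PK endpoints will be descriptively summarized as described in" its Section 11. SAP 11.5 gives the statistics: "Pharmacokinetic parameter data will be descriptively summarized using: N, Mean, SD, CV%, Min, Median, Max", followed by the geometric mean, geometric CV and a 95% CI. It lists no count or percentage above 20.0%.

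SAP 16.3.2 has two quality rules for parameters that depend on lambda-z:

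- **Fit rule.** Rsq should be at least 0.800, and "the observation period over which the regression line is estimated should be at least two-fold the resulting" half-life. If either criterion fails, the rate constant and the parameters derived from it, AUCextra% included, "will be included in the parameter outputs and descriptive statistics but will be flagged and discussed appropriately".
- **Extrapolation rule.** AUCextra% should not exceed 20.0%. If it does, AUC0-inf, AUCextra%, lambda-z, t1/2, Vz/f and CL/f "will not be included in the calculation of descriptive statistics or statistical analyses". This rule comes second and is tied to pivotal studies such as BE trials.

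The same section lists parameters for every volunteer with enough data and provides the NCA core output as a separate listing. SAP 11.1 leaves the format and content of tables to shells, which are not among the documents.

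**The concern.** Dropping an uncertain AUC0-inf or t1/2 when too much of the area is extrapolated protects those summaries. Dropping AUCextra% on the same trigger is different, because AUCextra% is the quantity that shows how much was extrapolated. Its summary is then cut off at the limit against which a reader would compare it.

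At stake is what the clinical study report conveys about the 48 h sampling. If some profiles breach 20.0%, the table looks better than the data, and someone reading only the table could take the Max as evidence that the limit was met. N would be smaller, but it also falls when lambda-z cannot be estimated (the SAP requires at least three terminal-phase points), so a smaller N does not say which happened.

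**Working it through.** The plan gives no figure to reproduce. The main result follows from the text; the numbers below only show its possible size.

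**1. Effect on the table.** Only values x ≤ 20.0 are tabulated, so Min, Median, Mean, geometric mean and Max are all at most 20.0. Let q be the fraction dropped. Then

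full mean − tabulated mean = q × (mean of dropped − mean of kept).

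Every dropped value is larger than every kept value, so this is positive whenever q > 0.

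Example with invented values 4, 6, 7, 8, 9, 11, 12, 15, 18, 22, 27, 35:

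- All 12: mean 174/12 = 14.5, median 11.5, maximum 35.
- Tabulated: N = 9, mean 90/9 = 10.0, median 9.0, maximum 18.
- Check: q = 3/12, dropped mean 84/3 = 28, and 0.25 × (28 − 10) = 4.5 = 14.5 − 10.0.

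**2. Half-life at which the rule acts.** The documents give no metformin half-life and no LLOQ. The only bound is indirect: Protocol 6.3.1 cites a washout of at least 7 half-lives and sets 7 days, so 168/7 = 24 h. That is a ceiling, not an estimate. Let s be the share of AUC0-inf carried by the terminal exponential and h the half-life:

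AUCextra% = 100 × s × exp(−ln 2 × t_last / h), so the threshold is h* = ln 2 × t_last / ln(s / 0.20).

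With t_last = 48 h (the last planned sample), ln 2 × 48 = 33.27:

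- s = 0.70: 33.27 / ln 3.5 = 33.27 / 1.253 = 26.6 h.
- s = 0.50: 33.27 / ln 2.5 = 33.27 / 0.916 = 36.3 h.
- One-compartment curve with fast rate 0.4/h: s is replaced by 0.4 / (0.4 − lambda-z), and the threshold is 19.5 h.

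At h = 24 h a breach needs s above 0.20 × 2^(48/24) = 0.80. An earlier t_last lowers thresholds: for s = 0.70 and t_last = 36 h, 26.6 × 36/48 = 19.9 h.

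**3. How often, under assumptions.** Simulated log-normal half-lives, 40% CV, t_last 48 h; percentage of profiles above 20.0%:

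| Assumed median half-life | One-compartment | s = 0.70 | s = 0.50 |
|---|---|---|---|
| 6 h | 0.1 | 0.0 | 0 |
| 8 h | 1.0 | 0.1 | 0 |
| 12 h | 10 | about 2 | 0.2 |
| 16 h | 30 | 9.4 | 1.7 |

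Of the 54 × 2 = 108 planned profiles, 1.0% is about 1 and 30% about 32. At 16 h the mean AUCextra% would be 15.8 but shown as 10.3 (one-compartment), 10.1 shown as about 8.5 (s = 0.70), and 7.2 shown as 6.9 (s = 0.50). With 20% CV at 16 h the exclusions are 16%, 0.5% and 0%. Every exclusion in the last two columns comes from a simulated half-life above 26.6 h or 36.3 h. If individual half-lives stay at or below 24 h, both columns are zero.

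**4. Overlap with the fit rule.** The SAP fixes the end of the window: "The last quantifiable concentration should always be included in the regression analysis". Suppose the terminal phase is log-linear and the window spans at least two half-lives. The fitted line then starts at 4 × C_last or higher, and the area inside the window is at least (4 − 1) × C_last/lambda-z. The extrapolated area is C_last/lambda-z, so AUCextra% is at most 1/(1 + 3) = 25%. Every profile above 25% therefore also fails the two-half-life criterion and would be flagged. Between 20% and 25% it depends on the profile.

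**The case against.** **A breach is not hidden.** Individual values stay in the parameter listing and the NCA output. Step 4 shows that many breaching profiles would also be flagged and discussed. This stands, with one limit: the flag records a short regression window, not the breach.

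**The shells may already hold a count.** They set table content and could not be checked. A reader might infer that the report can never show a breach; the documents do not support that. What stands is narrower: Mean and Max are cut off at 20.0%, and SAP 11.5 lists no count.

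**The rule can be read as coherent.** If a profile's extrapolation is judged unreliable, everything built on that lambda-z goes, and neither document says the AUCextra% table exists to test the limit. That is fair for the other five parameters. It does not remove the bias in the summary of AUCextra%.

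**The two rules conflict.** A reader might infer that SAP 16.3.2 contradicts itself, since one rule keeps what the other drops. The extrapolation rule is later, stricter and specific to BE trials, so it naturally prevails. It alone governs the AUC0-inf model, because the fit rule speaks only of parameter outputs and descriptive statistics. One line of clarification is enough.

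**The SAP departs from the protocol without saying so.** Protocol 9.4.3 has no 20% exclusion and SAP Section 9 declares no changes. But Protocol 9.4.1 leaves analysis detail to the SAP, so an undeclared change is not established.

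**Conclusion.** The point holds as a minor reporting defect. If any profile exceeds 20.0%, the planned summary of AUCextra% gives a Mean that is too low and a Max that cannot exceed the limit. That follows from the SAP wording alone.

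Its practical size is unknown. With t_last at 48 h there is no practical effect at assumed median half-lives of 6 to 8 h. For terminal phases carrying 70% or less of AUC, the rule needs half-lives above the 24 h that the washout implies. The larger figures rest on a 16 h median, a wide spread and a one-compartment shape, none of which the documents support in particular.

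A reader might infer that bioequivalence is in doubt. It is not: AUC0-t and Cmax do not use lambda-z.

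**What to change.** In SAP 16.3.2, take AUCextra% off the exclusion list and keep the 20.0% exclusion for AUC0-inf, lambda-z, t1/2, CL/f and Vz/f. Possible wording:

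> AUCextra% is summarised for all PK Population profiles with an estimable lambda-z. The number of profiles above 20.0% and the number not estimable are shown by product and food group.

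Optionally add that, for the other five parameters, the 20.0% exclusion takes precedence over keep-and-flag when a profile meets both. If the shells already contain these counts, only the exclusion list needs editing.

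The cost is a wording change and two table rows, with no new data and no change to the primary analysis. The downside is that some less certain extrapolated values appear in the summary. If no profile breaches the limit, no AUCextra% statistic changes.

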Glucophage® Extended Release (GXR) tablet contains metformin hydrochloride, an active pharmaceutical ingredient that belongs to the biguanide group antihyperglycemic drugs used in the management of type 2 diabetes mellitus (T2DM). Metformin has been used for clinical management of diet-failed T2DM patients since 1959 and is presently authorized in 140 countries and marketed in 127 of them. Complete information on the chemistry, pharmacology, efficacy, and safety of GXR tablet is in the Investigator's Brochure (IB) [1].

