2.2.2 Glucophage Extended Release

Glucophage (metformin hydrochloride: N,N-dimethylimidodicarbonimidic diamide hydrochloride; 1,1-dimethylbiguanide hydrochloride; N,N-dimethylbiguanide hydrochloride; N'- dimethylguanylguanidine hydrochloride) is an oral antihyperglycemic drug belonging to the class of biguanides and is not chemically or pharmacologically related to any other class of oral antihyperglycemic agents. The active ingredient, metformin, is the main representative of the biguanide class antihyperglycemic drugs.

Glucophage Extended Release tablet contains metformin hydrochloride, a white to off-white crystalline compound with a molecular formula of C₄H₁₁N₅ • HCl and a molecular weight of 165.62. Metformin hydrochloride is freely soluble in water and is practically insoluble in acetone, ether, and chloroform. It is an antihyperglycemic agent, which improves glycemic control in patients with T2DM. It does not stimulate insulin secretion and therefore does not produce clinically significant hypoglycemia. Metformin targets insulin resistance at the liver by decreasing hepatic glucose production and in muscle by enhancing peripheral glucose uptake and utilization, furthermore, it also delays intestinal glucose absorption. Metformin has been used for clinical management of diet failed T2DM patients since 1959. Over this time, extensive experience has been gathered relating to the clinical use and safety of metformin. Currently, there are different approved pharmaceutical forms of Glucophage, which have been developed to offer patients options that may fit their lifestyle and thereby improve compliance. Refer to the IB [1] for further information about the nonclinical and clinical programs of GXR and guidance for the Investigator.

2.3

Benefit/Risk Assessment

Metformin has been demonstrated by extensive clinical experience to be well tolerated in diabetic and prediabetic individuals with an acceptable safety profile. The most common side-effects observed in association with metformin are mild to moderate gastrointestinal events, which occur mainly during initiation of therapy and resolve spontaneously in most cases. Serious side-effects under treatment with metformin are very rare and generally limited to the condition of lactic acidosis, which is very rare and occurs primarily in patients with diabetes with acute deterioration of renal function or severe renal failure.

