6.1 Study Interventions Administration

6.1.1 Description of the Study Interventions

All IMPs will be sourced from respective manufacturer as listed below (Table 4). All IMPs will be packaged and labeled per all applicable regulatory requirements and Good Manufacturing Practice Guidelines.

Table 4 Information of Study Interventions

Drug Treatment	Test Product	Reference Product
Product Name:	GXR (Metformin HCL XR)	GXR (Metformin Hydrochloride Extended-release Tablets)
Formulation:	Tablet	Tablet
Strength:	0.5 g	0.5 g

Manufacturer:	Merck Nantong, China (Merck KGaA)	Merck Darmstadt, Germany (Merck KGaA)
Expiry Date:	Refer to the label content	Refer to the label content
Storage Condition:	According to medication label	According to medication label

GXR = Glucophage Extended Release.

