8.5 Pharmacokinetics

For metformin, blood samples will be collected by indwelling cannula (short-term peripheral catheter) for the first day and by direct venipuncture for the rest of the time. All blood samples should be processed within 30 minutes (centrifuge each tube for 10 minutes at 2000 g) or otherwise should be kept in an ice water bath pending processing.

For every participant, during each treatment period, a total of 17 samples, approximately 3 mL each whole blood, will be collected at the following times ([Table 6](#)):

- at predose (Baseline) and at 0.5, 1, 2, 3, 4, 5, 6, 7, 8, 10, 12, 14, 24, 30, 36, and 48 hours after dosing.
- One sample will be collected at Premature Withdrawal if applicable.

Eligible participants will have their Baseline blood sample collected at approximately 10 minutes before GXR administration in Periods 1 and 2 for both the fasting and fed group participants.

The PK collection time is based on known single-dose PK profiles of the extended release formulation and should be frequent and long enough to characterize the peak and extent of exposure. Plasma samples will be prepared, divided into 2 aliquots and stored at -20°C or lower.

Participants who complete both treatment periods will have a total of 34 samples (approximately 3 mL whole blood each sample) collected. Total PK blood volume collection is approximately 102 mL over 2 weeks.

A validated bioanalytical method will be applied to analyze plasma concentration of metformin. The assay and all related procedure will be developed and cross-validated with previously established methods to ensure quality standard and technical specifications are met. Details of the assay will be provided in the analytical plan separately.

The clock time of all blood draws will be recorded and reported for each participant in the eCRF. The actual sampling times, if available, will always be used for calculation.

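### The SAP treats the 500 mg dose as free drug for CL/f and Vz/f, but the protocol describes the tablet as metformin hydrochloride; absolute values could be overstated by 0% to 28.2%

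*SAP*

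**What the plan says.** SAP Section 16.3.2 defines CL/f as dose over AUC0-∞ and says: "The dose amount to be used for this calculation is 500 mg". Vz/f is dose over AUC0-∞ times λz. Near the end of the section the SAP gives the basis for the dose figure: "The dose amount for IMP administered is that of the active, free drug substance only, and is synonymous with the measured analyte". It then concludes: "No adjustment for the dose amount value of IMP will be applied" in formulas that need a dose.

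The protocol describes the substance differently. Section 2 (Introduction) says the "tablet contains metformin hydrochloride, an active pharmaceutical ingredient". Section 2.2.2 gives the formula C4H11N5 • HCl "and a molecular weight of 165.62". Table 4 in Section 6.1.1 names the test product "Metformin HCL XR" and the reference product "Metformin Hydrochloride Extended-release Tablets", each with a strength of 0.5 g.

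On the assay, Protocol Section 8.5 says: "A validated bioanalytical method will be applied to analyze plasma concentration of metformin". It leaves the details to a separate analytical plan. SAP Section 6 also refers only to metformin concentrations.

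**The concern.** A hydrochloride salt is not the free drug substance. The no-adjustment rule is right only if the dose mass and the plasma concentrations refer to the same chemical form. The SAP asserts that they do, but the protocol's product description does not support it, and neither document gives a free-base strength or a salt factor.

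Two facts are left open. The first is whether 0.5 g is a mass of salt or of base: Table 4 points to salt, and the SAP says free drug. The second is whether concentrations are expressed as metformin base: the SAP sentence implies so, but the assay text says only metformin.

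CL/f and Vz/f are declared secondary endpoints and the only planned parameters that use a dose. If the strength is salt and the concentrations are base, each tabulated value divides a salt mass by a base AUC, under a statement that the two are the same substance. A constant factor of this kind would not show in CV% or in any test/reference comparison, so nothing in the output would reveal it. SAP Section 5 intends the results for the study report and for regulatory submissions or manuscripts.

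**Working it through.** **Inputs**

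- Calculation dose: 500 mg (SAP 16.3.2).
- Hydrochloride formula C4H11N5 • HCl, molecular weight 165.62 (Protocol 2.2.2).
- Strength of both products: 0.5 g, with no statement of salt or base (Protocol Table 4).
- Standard atomic weights, not given in the documents: C 12.011, H 1.008, N 14.007, Cl 35.453.

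**Reproducing the protocol's molecular weight**

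- Base: 4 × 12.011 + 11 × 1.008 + 5 × 14.007 = 129.167.
- HCl: 1.008 + 35.453 = 36.461.
- Sum: 165.628, against 165.62 stated. They agree to within 0.008, so the stated figure is the molecular weight of the salt.

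**Salt-to-base factor, using the protocol's figure**

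- Base: 165.62 − 36.461 = 129.159.
- Base/salt: 129.159 / 165.62 = 0.780.
- Base content of 500 mg of hydrochloride: 500 × 129.159 / 165.62 = 389.9 mg.

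**Effect on the parameters**

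CL/f = Dose / AUC0-∞ and Vz/f = Dose / (AUC0-∞ × λz) are both proportional to dose, so a mismatch of scales multiplies every value by the same factor.

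| Basis of the 0.5 g | Concentrations expressed as | Effect on CL/f and Vz/f |
|---|---|---|
| Salt | Base | 165.62 / 129.159 − 1 = +28.2% |
| Salt | Salt | 0% |
| Base | Base | 0% |
| Base | Salt | 129.159 / 165.62 − 1 = −22.0% |

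Nothing in the documents points to the last row, so the supported range is 0% to +28.2%.

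**What does not change**

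Take illustrative (assumed) AUC0-∞ values of 5000 ng·h/mL for test and 5200 ng·h/mL for reference.

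- With 500 mg, CL/f is 100.0 and 96.2 L/h, ratio 1.04.
- With 389.9 mg, CL/f is 78.0 and 75.0 L/h, ratio 1.04.

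The factor cancels between products, and the same holds for Vz/f. It also cancels in CV% and GeoCV%, because SD and mean scale together. AUC0-t, Cmax, AUC0-∞, AUCextra%, tmax, t1/2 and λz contain no dose term.

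**The case against.** The strongest reply is that no contradiction is proven. A tablet can contain a salt while its strength is expressed as base. Table 4 gives product names and an unqualified 0.5 g, and the SAP does state a basis: dose and analyte are one substance. On that text alone the error is zero. The protocol also refers loosely to a dose of metformin (Section 4.3) and to metformin as the active ingredient (Section 2.2.2). The matter can be settled only from the label and the analytical plan, which are not part of these documents. The effect is confined to two apparent parameters that are summarised descriptively (SAP 16.2), and because the SAP discloses both the 500 mg and the absence of adjustment, a reader who knows the scales could rescale.

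Much of this stands. Nothing in the documents calls 0.5 g a salt mass, 28.2% is an upper bound and not an established error, and this is a question of consistency between documents more than of faulty arithmetic. It does not remove the point. The SAP states as fact something that the protocol's description of the product does not support, and builds a calculation rule on it. The loose references to metformin do not assign the 500 mg to base. A reader can rescale only if told the two scales, and the one sentence that addresses them is the one in doubt.

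**Conclusion.** The concern holds, at minor severity. The SAP's no-adjustment rule rests on a premise that conflicts with the protocol's description of both products as metformin hydrochloride, and the two have not been reconciled. The possible overstatement of every absolute CL/f and Vz/f is 0% to 28.2%. The upper end requires both that 0.5 g is salt and that concentrations are expressed as base; if dose and concentrations are on one scale, the values are correct and only the wording needs support. Confidence is high in the conflict and in the range, not in any single size of error. Bioequivalence conclusions do not depend on it.

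**What to change.** First settle two facts: from the product label, whether 0.5 g is metformin hydrochloride or metformin base; and from the analytical plan, how plasma concentrations are expressed. State both in SAP Section 16.3.2, so that it agrees with Protocol Sections 2, 2.2.2 and 6.1.1.

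- **If the strength is salt and the concentrations are base:** delete the sentence equating dose and analyte. Then either use the base equivalent (389.9 mg) as the constant in the CL/f and Vz/f formulas, or keep 500 mg and label both parameters as expressed per metformin hydrochloride dose.
- **If dose and concentrations are already on one scale:** keep 500 mg and correct or support the wording. Using 389.9 mg in this case would itself understate both parameters by 22.0%.

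This concerns a calculation constant and its label; the administered dose is not in question. The cost is a check of two existing documents, one or two SAP sentences, and possibly one constant in the WinNonlin set-up or one table footnote.
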